11.7.2. Handling of Missing Data

Element	Reporting Detail
General	
 • Missing data occurs when any requested data is not provided, leading to blank fields on the collection instrument: 
 ○ These data will be indicated by the use of a “blank” in participant listing displays. Unless all data for a specific visit are missing in which case the data is excluded from the table. ○ Answers such as “Not applicable” and “Not evaluable” are not considered to be missing data and should be displayed as such.
Growth Analyses	
Missing height data for the primary and supportive analyses of growth velocity described in Section 7: Growth Analyses, will not be imputed and will be treated as missing (assuming MAR).
 
For the supportive analysis defined in Section 7.1.6, two approaches have been defined to assess the effect of missing data. For these analyses, the population of interest will be the Intent-to-Treat (ITT) population, as defined in Section 4: Analysis Populations.
 
The final Week 52 (Visit 18) height measurement is scheduled for day 365 with a visit window of -5/+2 days. In cases where the final height measurement at week 52 is missing, (i.e. there is not a scheduled or unscheduled height measurement available for any of days 360 to 367 inclusive) the missing height measurement will be imputed at day 365 using Multiple Imputation based on two different approaches:
 
Approach 1: Use the ‘worst growth rate’ (i.e., smallest growth velocity) from participants from the FF 50 treatment group who complete the double-blind treatment period as the central value for imputations of missing data in the FF treatment group, and the ‘worst growth rate’ from participants from the placebo group who complete the double-blind treatment period as the central value for imputations of missing data in the placebo treatment group (Supportive Estimand IX).
 
Implementation of Approach 1: The steps are the same in both treatment arms, so the method for one arm will be described below:
 
Let y_{it} be the value of the height measurement of participant i at day $t = 0, \dots, 365$. Assume there are n participants in this treatment arm and of those: n_{obs} have a week

Element	Reporting Detail
	
52 height observed (i.e. at least one height measurement observed between days 360 and 367 inclusive, $y_{i,365}$) and n_{miss} have it missing. The steps to follow will be:
 
A. For every participant $i = 1, \dots, n_{obs}$ with observed week 52 height value (i.e., $y_{i,365}$), fit a regression model $y_{it} = \alpha_i + \beta_i t$, using all available height data. The estimated value $\hat{\beta}_i$ (i.e., slope) is the growth rate of that participant i and is the outcome that will be included in the planned statistical analysis. Let $\hat{\beta}_W$ be the worst estimated growth rate, i.e. $\hat{\beta}_W = \min\{\hat{\beta}_1, \dots, \hat{\beta}_{n_{obs}}\}$.
 
B. Let M be the number of imputations. For each imputation $m = 1, \dots, M$:
 
 • Step 1: For every participant $j = 1, \dots, n_{miss}$ with missing week 52 height, the missing week 52 height value $y_{j,365}^{(m)}$ will be imputed at day 365 by drawing a random value from a Normal distribution $N(\mu_{j,365}, \sigma^2)$, where: 
 ○ $\mu_{j,365} = y_{\tilde{t}_j} + \hat{\beta}_W \cdot (365 - \tilde{t}_j)$, where \tilde{t}_j is the last day with an observed height for participant j. Note that $\mu_{j,365}$ represents the expected height at day 365 assuming the participant would grow at the ‘worst’ observed growth rate between the last day their height was measured and day 365. ○ The variance σ^2 is the estimated variance of heights at day 365, which is estimated by fitting a regression model to all heights from all n_{obs} subjects and extract the residual variance as σ^2. Note that the imputed height value $y_{j,365}^{(m)}$ must be equal or larger than the last observed height value $y_{j\tilde{t}_j}$ which means that a value from a truncated Normal should be drawn. • Step 2: For every participant $j = 1, \dots, n_{miss}$, fit a regression model $y_{jt} = \alpha_j + \beta_j t$ using all the observed and imputed height data $y_{j0}, \dots, y_{j\tilde{t}_j}, y_{j,365}^{(m)}$ of participant j to obtain the estimated value of the growth rate $\hat{\beta}_j^{(m)}$ for participant j. This value will be the ‘imputed’ growth rate for participant j in the m^{th} imputed dataset. 
After completing steps A and B, each imputed dataset $m = 1, \dots, M$ will have observed growth rates $\hat{\beta}_i, i = 1, \dots, n_{obs}$ and imputed growth rates $\hat{\beta}_j^{(m)}, j = 1, \dots, n_{miss}$. These $\hat{\beta}$’s will be the endpoint of growth velocity to be analysed. The same ANCOVA model as the one used for the primary analysis (Section 7.1.5) will be used. The M results (i.e., mean treatment difference in growth velocities between the two arms, and associated CI) will be combined using Rubin’s rules as implemented in Proc MIANALYZE.
 
Approach 2: Use the ‘worst growth rate’ (i.e. smallest treatment velocity) from participants from the FF 50 treatment group who complete the double-blind treatment period as the central value for imputations of missing data in the FF treatment group, and assume any data missing in the placebo treatment group are missing at random (Supportive Estimand X).


Element	Reporting Detail																																									
	
Implementation of Approach 2: For the FF 50 arm proceed as in approach 1. For the placebo arm the process simplifies to fitting a regression model $y_{it} = \alpha_i + \beta_i t$ for each of the n participants in the arm using their available height data (i.e. no distinction between participants who have and do not have the week 52 height observed). The estimated value β_i is the growth rate of participant i and is the endpoint of growth velocity to be analysed. The same ANCOVA model as the one used for the primary analysis (Section 7.1.5) will be used. The M results (i.e., mean treatment difference in growth velocities between the two arms, and associated CI) will be combined using Rubin's rules as implemented in Proc MIANALYZE.
																																									
eDiary Data & 24-hour periods	
 Efficacy endpoints relating to daily diary assessments will be calculated from all available data over the time period of interest. No imputations will be performed on missing daily diary data. The Table below shows how missing data will be considered with respect to symptom- and rescue-free 24-hour periods. 
  
 Symptom Scores	24-hour Period	
 
 AM	PM	
   
 >0	0	Not symptom-free	
 
 0	>0	Not symptom-free	
 
 0	0	Symptom-free	
 
 0	Missing	Missing	
 
 Missing	0	Missing	
 
 >0	Missing	Not symptom-free	
 
 Missing	>0	Not symptom-free	
 
 Missing	Missing	Missing	
 
 Rescue medication use (puffs)		
 
 0	Rescue-free	
 
 >0	Not rescue-free	
 
 Missing	Missing	
  
	Symptom Scores		24-hour Period	AM	PM	>0	0	Not symptom-free	0	>0	Not symptom-free	0	0	Symptom-free	0	Missing	Missing	Missing	0	Missing	>0	Missing	Not symptom-free	Missing	>0	Not symptom-free	Missing	Missing	Missing	Rescue medication use (puffs)			0		Rescue-free	>0		Not rescue-free	Missing		Missing
Symptom Scores		24-hour Period																																								
AM	PM																																									
>0	0	Not symptom-free																																								
0	>0	Not symptom-free																																								
0	0	Symptom-free																																								
0	Missing	Missing																																								
Missing	0	Missing																																								
>0	Missing	Not symptom-free																																								
Missing	>0	Not symptom-free																																								
Missing	Missing	Missing																																								
Rescue medication use (puffs)																																										
0		Rescue-free																																								
>0		Not rescue-free																																								
Missing		Missing																																								

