9.2. Sample Size Considerations

9.2.1. Sample Size Assumptions

The proposed sample size for this study is based on FDA guidance [[Guidance for Industry Orally Inhaled and Intranasal Corticosteroids: Evaluation of the Effects on Growth in Children](#), March 2007].

The study is not powered to detect any treatment differences. The study is designed to provide the estimated mean treatment difference between inhaled FF 50 mcg once daily (OD) (plus montelukast open-label) and inhaled placebo (plus montelukast open-label) in prepubescent growth velocities, with a certain degree of precision on the 95% confidence interval. The primary population for growth analyses will be the Growth Population (defined in Section 9.3.1). An analysis of covariance (ANCOVA) model will be used to estimate the mean treatment difference in growth velocities over the double-blind treatment period, adjusting for baseline growth velocity, age at Visit 1, gender, and country. A 95% confidence interval will also be provided for the estimated mean treatment difference in growth velocity over the double-blind treatment period (Section 9.4.1).

Eligible subjects will be stratified by country and randomised in a 1:1 ratio to inhaled FF 50 mcg OD (plus montelukast open-label) or inhaled placebo (plus montelukast open-label). At least 450 subjects will be randomised (approximately 225 per treatment arm). Assuming a withdrawal rate from study medication of up to 10% within the first 12 weeks, this would still ensure at least 406 eligible subjects (approximately 203 per treatment arm) for inclusion in the Growth Population (Section 9.3.1) analyses. Assuming a standard deviation for the growth velocities of 1.2 cm/year (based on study FFR101782), a sample size of 203 eligible subjects per treatment arm ensures the width of the confidence interval for the mean treatment difference is no greater than 0.5cm/year (Section 9.2.2).

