7.1.4. Strategy for Intercurrent (Post-Randomisation) Events

The primary treatment effect to be estimated is the treatment policy effect of initial randomised treatment. The list of intercurrent events/events leading to missing data that may occur during the study and may affect the estimation of the treatment effect are:

- **Discontinuation of Randomised Treatment:** Participants may prematurely discontinue double-blind treatment and continue in the study. This is considered an intercurrent event.
- **Participants Presenting Tanner Stage ≥ 2 :** Participants must be pre-pubertal (Tanner Stage 1) at the time of randomisation but may present physical characteristics of Tanner Stage 2 or higher at any point during the study. This is considered an intercurrent event.
- **Use of Rescue Systemic Corticosteroids:** Participants may receive rescue systemic corticosteroids at any point during the study. This is considered an intercurrent event.
- **Use of Rescue Inhaled/Intranasal Corticosteroids:** Participants may receive rescue inhaled/ intranasal corticosteroids at any point during the study. This is considered an intercurrent event.
- **Early Withdrawal from Study:** Participants may prematurely withdraw from the study which results in missing endpoint data.
- **Week 52 Height Not Available (other reasons than early withdrawal):** Height information at Week 52 may not be available for other reasons (not Early Withdrawal).

All available data up to the time of study withdrawal will be included in the primary analyses, regardless of discontinuation of randomised treatment, use of rescue corticosteroids, or Tanner Stage. To minimize study withdrawals, participants who

discontinue randomised treatment will be encouraged to stay in the study and complete all remaining protocol-specified visits and be followed-up as per the protocol until the completion of follow-up assessments. All non-missing data will be included in the primary analyses. Missing data will be assumed missing at random (MAR) in the primary analysis and will not be imputed. Missing data will be imputed in sensitivity analyses as described below in Section 7.1.6.

The strategies for handling these events for this endpoint are described in the below Table.

Event	Handling Strategy
Discontinuation of Randomised Treatment	Available height data will be used in the analysis, regardless of early discontinuation of randomised treatment.

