Discontinuation of Randomised Treatment	Only available height data while the participant is on randomised double-blind treatment will be used in the analysis.								
Event	Handling Strategy								
Discontinuation of Randomised Treatment	Only available height data while the participant is on randomised double-blind treatment will be used in the analysis.								

Supportive Estimand VIII for Primary Endpoint
									

 • Another supportive estimand defined for the primary endpoint (as defined in Section 7.1.1) will be Supportive Estimand VIII. • This estimand will be based on the ITT Population (as defined in Section 4: Analysis Populations). • The summary measure will be as described in Section 7.1.2 for the primary analysis, and the statistical analyses/methods (i.e., model specification, model checking and diagnostics, and model results presentation) will be as described in Section 7.1.5 for the primary analysis. • The strategies for handling the intercurrent events/events leading to missing data for this estimand will be as described in Section 7.1.4 for the primary analysis. 									

Supportive Analyses - Assessing Missing Data
									

 • Two approaches have been defined to assess the effects of missing data. For these analyses the population of interest will be the Intent-to-Treat (ITT) population, as defined in Section 4: Analysis Populations. • In cases where the final height measurement at week 52 is missing, these missing height data will be imputed using Multiple Imputation (described at length in Section 11.7.2) by applying to the last available height measurement the following sets of rules: 
 1. Use the ‘worst growth rate’ (i.e., smallest growth velocity) from participants from the FF 50 treatment group who complete the double-blind treatment period as the central value for imputations of missing data in the FF treatment group, and the ‘worst growth rate’ from participants from the placebo group who complete the double-blind treatment period as the central value for imputations of missing data in the placebo treatment group. 2. Use the ‘worst growth rate’ (i.e. smallest treatment velocity) from participants from the FF 50 treatment group who complete the double-blind treatment period as the central 									

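### The worst-growth imputation draws Week 52 heights with a between-child variance and truncates them at the last height, so Approach 2 loses most or all of its penalty on FF

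*SAP*

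**What the plan says.** SAP section 7.1.6 sets up the missing-data assessment: "Two approaches have been defined to assess the effects of missing data". These are Supportive Estimands IX and X, both in the ITT population. In Approach 1 each arm's missing Week 52 heights are imputed at that arm's smallest completer growth velocity. In Approach 2 only FF is treated this way, and placebo is left missing at random. Section 11.7.2 describes the worst FF rate "as the central value for imputations of missing data in the FF treatment group".

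The implementation in section 11.7.2 has these parts:

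- **Step A** fits a separate line to each completer, with that child's own intercept and slope, and takes the smallest slope as the worst rate.
- **Step 1, centre.** The Normal mean is the child's last height plus the worst rate times the remaining time. The SAP says this "represents the expected height at day 365 assuming the participant would grow at the" worst observed rate.
- **Step 1, variance.** The variance "is the estimated variance of heights at day 365, which is estimated by fitting a regression model to all heights from all" completers, taking the residual variance. The regressors are not given.
- **Step 1, truncation.** The imputed height must be at least the last observed height, "which means that a value from a truncated Normal should be drawn".
- **Approach 2.** "For the FF 50 arm proceed as in approach 1".

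The primary analysis lies outside this procedure: "Missing data will be assumed missing at random (MAR) in the primary analysis and will not be imputed" (SAP 7.1.4).

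**The concern.** The centre of the draw is a within-child prediction, because it starts from that child's own last height. The variance belongs to a different quantity, namely how much heights differ from child to child at Week 52. Eligible boys are 5 to under 9 years and girls 5 to under 8 (Protocol 5.1), so that spread is several centimetres even before same-age variation is counted. Growth over the rest of the year at the worst rate is only about 2 cm.

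A draw that wide, cut off below at the last height, keeps mainly its upper part. The average imputed child then grows much faster than the worst rate, and possibly faster than an ordinary child.

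Approach 2 is the analysis meant to be hard on FF in a study of growth suppression. If its penalty disappears or changes sign, an unchanged or smaller treatment difference would be read as robustness to missing data when nothing had been tested.

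**Working it through.** **The plan's own figure.** The SAP gives no number for the imputation. The nearest figure is the precision target in Protocol 9.2.1. With SD 1.2 cm/yr and 203 per arm, the half-width is 1.96 × 1.2 × √(2/203) = 0.233, so the width is 0.467 cm/yr. This agrees with the stated maximum of 0.5 and gives a scale for the shifts below.

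**How large is the SD of the draw?** The documents give no height SD. From age alone, with uniform ages over the eligible ranges and equal numbers of each sex:

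- Variance of age = ½(4²/12 + 3²/12) + 0.25² = 1.104, so the SD is 1.05 years (0.25 is half the difference between the mean ages, 7.0 and 6.5).
- At 5.9 cm/yr this is 1.05 × 5.9 = 6.2 cm.

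Adding an assumed same-age SD of 5 cm, cut at the 3rd and 97th centiles, gives about 7.6 cm for a regression on time only. If age and sex are also regressors, about 4.3 cm remains. Residuals about each child's own line are about 0.3 cm, the assumed visit error.

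**Mean of the truncated draw.** Let T be the remaining time in years, c = worst rate × T and σ the SD. Mean growth after the last height is c + σφ(c/σ)/Φ(c/σ), and the share cut off is Φ(−c/σ). For an assumed worst rate of 2.25 cm/yr and a last height at Week 12 (day 85), T = 280/365.25 = 0.767 and c = 1.725 cm:

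- σ = 7.6: 1.725 + 7.6 × 0.3888/0.590 = 6.74 cm, or 8.8 cm/yr.
- σ = 4.3: 1.725 + 4.3 × 0.3681/0.656 = 4.14 cm, or 5.4 cm/yr.
- σ = 0.3: 1.72 cm, or 2.25 cm/yr.

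| Last height | σ 7.6: cut, cm/yr | σ 4.3: cut, cm/yr | σ 0.3: cut, cm/yr |
|---|---|---|---|
| Week 4 | 39%, 7.5 | 32%, 4.7 | 0%, 2.25 |
| Week 8 | 40%, 8.1 | 33%, 5.0 | 0%, 2.25 |
| Week 12 | 41%, 8.8 | 34%, 5.4 | 0%, 2.25 |
| Week 28 | 45%, 14.0 | 41%, 8.3 | 0%, 2.25 |

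Imputed growth reaches the assumed FF mean (5.9 − 0.48 = 5.42 cm/yr) at σ = 5.2, 4.7 and 4.3 cm for Weeks 4, 8 and 12, and at 2.6 cm for Week 28. Above those values the worst-case child grows faster than the average FF child.

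**Simulated effect on Approach 2.** Settings: 225 per arm; true difference −0.48 cm/yr (the meta-analysis figure in Protocol 2.1); SD of true velocity 1.1; ANCOVA on baseline velocity, age and sex (country omitted); σ and worst rate re-estimated per arm in each replicate; M = 20; Rubin's rules; 200 replicates (120 at 15% missing). Monte Carlo SE is about 0.01, and up to 0.014 at 15%. Entries are FF minus placebo in cm/yr.

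| Missing, last height | No imputation | Time-only σ (7.6) | Age- and sex-adjusted σ (4.3) | Within-child σ (0.3) |
|---|---|---|---|---|
| 10%, Weeks 4–12 | −0.48 | −0.24 | −0.51 | −0.75 |
| 10%, Weeks 4–40 | −0.46 | −0.18 | −0.43 | −0.67 |
| 5%, Weeks 4–12 | n/a | −0.37 | −0.50 | −0.62 |
| 5%, Weeks 4–40 | n/a | −0.33 | −0.46 | −0.58 |
| 15%, Weeks 4–12 | n/a | −0.11 | −0.53 | −0.90 |
| 15%, Weeks 4–40 | n/a | −0.04 | −0.43 | −0.80 |

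(n/a: no comparator available.) In the first row the intended penalty is −0.75 − (−0.48) = −0.27. With σ = 4.3 it is −0.03, and with σ = 7.6 it becomes +0.24. With visit error 0.5 cm (100 replicates, early dropout, 10%) the estimates are −0.28 time-only, −0.79 within-child and −0.50 without imputation.

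**Approach 1, time-only against within-child σ.**

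- Equal 10% missing: −0.45 against −0.47 (early), −0.44 against −0.46 (spread).
- FF 10%, placebo 5%, spread: −0.34 against −0.60 (no imputation −0.50).
- FF 5%, placebo 10%, spread: −0.61 against −0.38 (no imputation −0.48).

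The distortion cancels only when missingness is balanced.

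**A second simulation** used no true difference, mean 6 cm/yr, no covariates and M = 10. At 10% missing with early dropout, Approach 2 should give −0.20. It gave −0.01 (adjusted SD 4.0), +0.08 (adjusted SD 5.0) and +0.35 (time only, SD about 8.5). The within-child variance returned −0.20.

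**The case against.** The strongest reply is that the variance regression is not written out. Every regression that section 11.7.2 does write out has child-specific coefficients. If that form was meant, the residual is about 0.3 cm and the method works. This reading is possible. However, the sentence carries no child index, describes one model over all completers' heights, and calls the result a variance of heights at day 365. Scatter about a child's own line is not that, and a programmer following the text would not compute it.

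Other points stand in part:

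- The sentence on expected height describes the Normal mean before truncation, and that value remains the mode. After truncation it is no longer the expected height, so the worst rate is not the centre of what is imputed.
- Protocol 9.2.1 refers to stopping medication: "Assuming a withdrawal rate from study medication of up to 10% within the first 12 weeks". Protocol 5.5.1 asks such children to stay for the Week 52 height, so 10% missing is an assumption, and 5% and 15% are shown for that reason.
- Only two supportive estimands are affected, there is no hypothesis test, and the ITT analysis without imputation (Estimand VIII) is reported separately. That limits the consequence but does not repair the two analyses.
- A within-child variance makes the draws nearly deterministic. That is acceptable in a stress test whose purpose is to fix growth at the worst rate. The SD of slopes times the remaining time is an alternative, but the truncation would then have to be re-examined.

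**Conclusion.** The concern holds. Followed as written, Step 1 does not impute at the worst growth rate, and Approach 2 does not apply the penalty it was designed to apply. At 10% missing with early dropout, the FF penalty shrinks from about −0.27 to about −0.03 cm/yr if the regression includes age and sex; that is blunting, not reversal. With later dropout at the same σ it turns slightly towards FF (−0.43 against −0.46 without imputation). With a time-only regression it reverses clearly, to about +0.24 with early dropout. The gap between the intended and the literal result, 0.24 to 0.51 cm/yr in that early-dropout case, is comparable with the 0.48 cm/yr class effect cited in the protocol.

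These sizes depend on assumed height SDs, visit error, worst rate, and amount and timing of missing Week 52 heights. The direction depends only on the variance being pooled over children, which is the plain reading. Approach 1 is affected mainly when missingness differs between arms. The primary analysis is not affected. This should be corrected before unblinding.

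**What to change.** In Step 1, define the variance as the pooled within-child residual variance from the Step A completer fits: the residual sums of squares added over completers, divided by their pooled degrees of freedom. Keep the lower truncation, which then hardly ever acts. If this was always the intention, the same sentence makes it explicit.

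Before unblinding, run the procedure on blinded data with dummy treatment codes and confirm that mean imputed growth after the last height is close to the worst rate.

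The cost is a one-sentence SAP edit and one line of code, with no new data and no additional children.
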